**Table 6.4.1 Management of Treatment-Emergent Hypertension**

Grade (CTCAE v 4.03)	Antihypertensive Therapy	Regorafenib or placebo Dosing
G 1 Prehypertension (systolic BP 120 - 139 mmHg or diastolic BP 80 - 89 mmHg)	None	
 
• Continue regorafenib or placebo
 
• Consider increasing blood pressure (BP) monitoring
 

G 2 Systolic BP 140 - 159 mmHg or diastolic BP 90 - 99 mmHg, OR Symptomatic increase by > 20 mmHg (diastolic) if previously within normal limits	
 
• Treat with the aim to achieve diastolic BP ≤ 90 mm Hg:
 
• If BP previously within normal limits, start anti-hypertensive monotherapy
 
• If patient already on anti-hypertensive medication, titrate up the dose.
 
	
 
• Continue regorafenib or placebo
 
• If symptomatic, hold regorafenib or placebo until symptoms resolve AND diastolic BP ≤ 90 mm Hga. When regorafenib or placebo is restarted, continue at the same dose level.
 

G 3 Systolic BP ≥ 160 mmHg or diastolic BP ≥ 100 mmHg OR More than one drug or more intensive therapy than previously used indicated	
Treat with the aim to achieve diastolic BP ≤ 90 mm Hg: Start anti-hypertensive medication
 
AND/OR Increase current anti-hypertensive medication
 
AND/OR Add additional anti-hypertensive medications.
	
 
• Hold regorafenib or placebo until diastolic BP ≤ 90 mm Hg, and if symptomatic, until symptoms resolvea.
 
• When regorafenib or placebo is restarted, continue at the same dose level.
 
• If BP is not controlled with the addition of new or more intensive therapy, reduce by 1 dose levelb.
 
• If Grade 3 hypertension recurs despite dose reduction and antihypertensive therapy, reduce another dose levelc.
 

G 4 Life-threatening consequences (e.g. malignant hypertension, transient or permanent neurologic deficit, hypertensive crisis)	Per institutional guidelines	Discontinue therapy

a. Patients requiring a delay of > 4 weeks should will discontinue regorafenib or placebo and stop participation in the study.
 
b. If BP remains controlled for at least one cycle, dose re-escalation is permitted per investigator's discretion.
 
c. Patients requiring > 2 dose reductions should go off protocol therapy.
 
G: Grade
		

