## 6.4 Hypertension

Hypertension is a recognized AE associated with regorafenib treatment. Subject will have their blood pressure measured at least weekly at the study site on weeks 1, 2, 3, 5, and 7. If additional blood pressure measurements are done outside the study site, and the blood pressure is > 140 mm Hg systolic or > 90 mm Hg diastolic (NCI CTCAE v 4.03), then the subject must contact study personnel. The management of hypertension, including the choice of antihypertensive medication, will be performed according to local standards and to the usual practice of the investigator. Every effort should be made to control blood pressure by medical means other than study drug dose modification. If necessary, **Table 6.5** below outlines suggested dose reductions.

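### Table 6.4.1 holds drug for systolic pressure of 160 or more but releases on diastolic pressure alone, so an adult can restart at the same dose while still Grade 3

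*Combined protocol and SAP*

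**What the plan says.** All of the following is in Table 6.4.1 of the combined protocol and SAP, unless another place is named.

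- Grade 3 definition: "Systolic BP ≥ 160 mmHg or diastolic BP ≥ 100 mmHg". Either component is enough. A third route to Grade 3 is the need for more than one drug or for more intensive therapy than before.
- Grade 3 treatment aim: "Treat with the aim to achieve diastolic BP ≤ 90 mm Hg", by starting, increasing or adding antihypertensives.
- Grade 3 hold and release: "Hold regorafenib or placebo until diastolic BP ≤ 90 mm Hg, and if symptomatic, until symptoms resolve".
- Restart: "When regorafenib or placebo is restarted, continue at the same dose level".
- Next step: "If BP is not controlled with the addition of new or more intensive therapy, reduce by 1 dose level". The table does not define control.
- Grade 2 is "Systolic BP 140 - 159 mmHg or diastolic BP 90 - 99 mmHg" (or a symptomatic diastolic rise). Dosing continues if the patient has no symptoms. If there are symptoms, the instruction is to "hold regorafenib or placebo until symptoms resolve AND diastolic BP ≤ 90 mm Hg".
- Footnote a: a delay of more than 4 weeks ends treatment.

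Table 6.4.2, titled for pediatric patients, covers symptomatic Grade 2 and Grade 3 events. It releases patients aged 17 or under once symptoms have resolved and pressure is below the 95th percentile, which is tabulated for both components. For patients over 17 the pressure must be below 160/90.

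**The concern.** A hold should end when the finding that caused it has gone. Here one of the two pressures that can cause the hold plays no part in ending it. For an event driven by systolic pressure, the Grade 3 row as written permits restart at the same dose with no fall in systolic pressure at all.

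The synopsis lists hypertension among the trial's specific safety concerns. Adults in the open Cohorts D and E start at 160 mg daily (Section 6.1). At stake is the safety of adults whose hypertension is mainly systolic. The efficacy analysis is not involved.

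**Working it through.** No sample size, event count or error rate enters this point, so the check is a comparison of rules. S is systolic and D is diastolic pressure, in mm Hg.

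**Inputs, from the Grade 3 row of Table 6.4.1**

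- Trigger on pressure, T: S ≥ 160 or D ≥ 100.
- Release on pressure, R: D ≤ 90. Symptoms must also have resolved if there were any.
- Dose at restart: unchanged.

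**Do T and R overlap?** D ≥ 100 and D ≤ 90 cannot both hold, so a patient with raised diastolic pressure must fall by at least 100 − 90 = 10 mm Hg before release. S ≥ 160 and D ≤ 90 can both hold. The overlap is therefore every reading with S ≥ 160 and D ≤ 90.

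- 170/85, no symptoms: 170 is 10 above the systolic threshold, so drug is held. 85 is already at or below 90, so the release is met on the same reading. Grade fall required: 0.
- 185/105 treated to 165/88, no symptoms: 88 ≤ 90, so drug is released at the same dose. 165 is still 5 above the threshold, so the patient is still Grade 3.

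**How the protocol ends its other Grade 3 holds**

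| Table | Condition for restart | Fall required |
|---|---|---|
| 6.2 (excludes hypertension) | Grade 2 or less | at least 1 grade |
| 6.3.2, hand-foot skin reaction | Grade 0 or 1 | at least 2 grades |
| 6.5.1, ALT/AST | below 3 × ULN or baseline | from above 5 × ULN |
| 6.4.1, isolated systolic Grade 3 | diastolic ≤ 90 | 0 grades |

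The first three act on the measure that triggered the hold. The last does not.

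**How the protocol treats systolic pressure elsewhere.** Section 6.4 tells patients to call the study team when, away from the site, "the blood pressure is > 140 mm Hg systolic or > 90 mm Hg diastolic". Exclusion 3.2.10 also names both components. The release for patients over 17 in Table 6.4.2 needs pressure below 160/90. A patient at 165/88 fails that release and passes the one in Table 6.4.1. The protocol calls patients under 18 pediatric (Sections 5.4 and 6.1), so an entry for patients over 17 in a pediatric table leaves unclear which rule an adult falls under.

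**Check of the repair.** Let R′ be S < 160 and D ≤ 90. S ≥ 160 contradicts the first part and D ≥ 100 contradicts the second, so T and R′ share no reading.

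**Symptomatic Grade 2 row.** Its release is also diastolic only. A limit of S < 160 would add nothing there, because every systolic value from 140 to 159 already meets it.

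**The case against.** Several arguments on the other side carry weight.

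- **The table is not the only guide.** Section 6.4 leaves management to local standards and the investigator's usual practice, and calls the dose reductions suggested. Section 5.8 requires withdrawal where continuing would be harmful. This lowers the risk, but these texts permit stricter care without setting a systolic condition for ending the hold.
- **The not-controlled step.** It refers to blood pressure generally, so a patient still at systolic 160 or more after intensified therapy could naturally be read as not controlled and have the dose reduced. That reading is reasonable. It is not secured, because control is undefined and the only stated aim is diastolic. The step also changes the dose without extending the hold.
- **A deliberate policy.** Section 6.4 asks investigators to control pressure by means other than changing study drug dose. This helps explain why hypertension is handled less strictly than skin or liver toxicity, so the table of grade falls does not prove a defect by itself. It gives no reason to ignore one of the two components that trigger the hold.
- **Small reach.** Enrollment in Cohorts A to C is complete, Cohorts D and E total 24 patients, and Section 2.5 says most embryonal and alveolar rhabdomyosarcoma patients are children. This stands.

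Two stronger readings are tempting, and the documents do not support either. A reader might infer that the protocol contains no systolic release value. It does, in Table 6.4.2 for patients over 17; the trouble is that the value is missing from Table 6.4.1 and the two tables disagree. A reader might also infer from the contact threshold in Section 6.4 that release must wait for systolic 140 or less. That threshold prompts a call and is not a dosing rule. The limit would also keep an asymptomatic patient at 150/85 on hold, at a pressure where the Grade 2 row continues dosing.

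**Conclusion.** The point holds as a defect in a stated safety rule. Read literally, the Grade 3 row of Table 6.4.1 lets an asymptomatic adult with systolic pressure of 160 or more and diastolic pressure of 90 or less restart at the same dose while still Grade 3. It also conflicts with the release for patients over 17 in Table 6.4.2.

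The conclusion assumes that the row is followed as written and that Table 6.4.1 is the one used for adults. Investigator judgement may prevent the outcome in practice.

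The reach is small and cannot be counted. The background sections give Grade 3 or higher hypertension rates from earlier trials (7% in Section 2.4.1, 48.5% in Section 2.4.2), but nothing splits events into systolic and diastolic, and no adult share is given for Cohorts D and E. The number affected may be zero. Sample size, power and alpha do not change.

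**What to change.** In the next amendment:

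1. **Grade 3 release, Table 6.4.1:** require systolic below 160 mm Hg and diastolic at or below 90 mm Hg, plus symptom resolution if the patient had symptoms.
2. **Grade 3 aim:** add a systolic component beside the diastolic one.
3. **Control:** state that systolic 160 or more after intensified therapy counts as not controlled. Use the same meaning in footnote b, which allows re-escalation while pressure stays controlled.
4. **Table 6.4.2:** keep the release for patients over 17 until the systolic value is in Table 6.4.1, then align the two tables and state which ages each covers. Removing that entry first would delete the only systolic release value these tables give for that age group.

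Whether to go lower (systolic 140 or less), and whether to put any systolic value in the symptomatic Grade 2 release, are clinical choices for the sponsor.

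The cost is table wording. Blood pressure is already measured at visits, and the value of 160 is already in the protocol. Some adults would be held somewhat longer. That time counts toward the 4-week limit in footnote a and toward the Section 5.6 rule that ends treatment more than 28 days after the last dose.

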**Table 6.4.2 Management of Treatment Emergent Hypertension for pediatric patients**

**Please refer to appendix:**

Grade (CTCAE v 4.03)	Antihypertensive Therapy	Regorafenib or placebo Dosing
Grade 1 If age ≤ 17 years: Asymptomatic, transient (< 24 hrs) BP increase > ULN; intervention not indicated. If age > 17	Consider increased BP monitoring; start anti-hypertensive medication if appropriate	No modification

years: (SBP 120-139 mmHg or DBP 80-89 mmHg)		
Grade 2 asymptomatic If age ≤ 17 years: Recurrent or persistent (≥ 24 hrs) BP > ULN; If age > 17 years: (SBP 140-159 mmHg or DBP 90-99 mmHg)	-If age ≤ 17 years: monotherapy indicated, -If age > 17 years: As in Table 6.5	Continue Study drug
Grade 2 symptomatic OR Grade 3: (> 17 years: SBP > 160 mmHg or DBP > 100 mmHg) requiring more than one drug or more intensive therapy than previously (all ages)	• Start or adjust anti-hypertensive medication as in table 6.5	• Hold study drug until symptoms resolve AND BP < 95th percentile ULN for age, height, and gender, if age ≤ 17 years; or BP < 160/90 mmHg if age > 17 years. Resume study at 100% (full) dose. If similar toxicity recurs, discontinue study drug.
Grade 4 (all ages) life threatening (eg, hypertensive crisis or malignant hypertension)	Per institutional guidelines	Discontinue study drug

**90th and 95th PERCENTILE BLOOD PRESSURE BY PERCENTILE HEIGHT IN  
GIRLS AGE 1-17 YEARS**

Age (Year)	BP Percentile	Systolic BP (mmHg)							Diastolic BP (mmHg)						
		Percentile of Height							Percentile of Height						
↓		5th	10th	25th	50th	75th	90th	95th	5th	10th	25th	50th	75th	90th	95th
1	90th	97	97	98	100	101	102	103	52	53	53	54	55	55	56
	95th	100	101	102	104	105	106	107	56	57	57	58	59	59	60
2	90th	98	99	100	101	103	104	105	57	58	58	59	60	61	61
	95th	102	103	104	105	107	108	109	61	62	62	63	64	65	65
3	90th	100	100	102	103	104	106	106	61	62	62	63	64	64	65

	95th	104	104	105	107	108	109	110	65	66	66	67	68	68	69
4	90th	101	102	103	104	106	107	108	64	64	65	66	67	67	68
	95th	105	106	107	108	110	111	112	68	68	69	70	71	71	72
5	90th	103	103	105	106	107	109	109	66	67	67	68	69	69	70
	95th	107	107	108	110	111	112	113	70	71	71	72	73	73	74
6	90th	104	105	106	108	109	110	111	68	68	69	70	70	71	72
	95th	108	109	110	111	113	114	115	72	72	73	74	74	75	76
7	90th	106	107	108	109	111	112	113	69	70	70	71	72	72	73
	95th	110	111	112	113	115	116	116	73	74	74	75	76	76	77
8	90th	108	109	110	111	113	114	114	71	71	71	72	73	74	74
	95th	112	112	114	115	116	118	118	75	75	75	76	77	78	78
9	90th	110	110	112	113	114	116	116	72	72	72	73	74	75	75
	95th	114	114	115	117	118	119	120	76	76	76	77	78	79	79
10	90th	112	112	114	115	116	118	118	73	73	73	74	75	76	76
	95th	116	116	117	119	120	121	122	77	77	77	78	79	80	80
11	90th	114	114	116	117	118	119	120	74	74	74	75	76	77	77
	95th	118	118	119	121	122	123	124	78	78	78	79	80	81	81
12	90th	116	116	117	119	120	121	122	75	75	75	76	77	78	78
	95th	119	120	121	123	124	125	126	79	79	79	80	81	82	82
13	90th	117	118	119	121	122	123	124	76	76	76	77	78	79	79
	95th	121	122	123	124	126	127	128	80	80	80	81	82	83	83
14	90th	119	120	121	122	124	125	125	77	77	77	78	79	80	80
	95th	123	123	125	126	127	129	129	81	81	81	82	83	84	84
15	90th	120	121	122	123	125	126	127	78	78	78	79	80	81	81
	95th	124	125	126	127	129	130	131	82	82	82	83	84	85	85
16	90th	121	122	123	124	126	127	128	78	78	79	80	81	81	82
	95th	125	126	127	128	130	131	132	82	82	83	84	85	85	86
17	90th	122	122	123	125	126	127	128	78	79	79	80	81	81	82
	95th	125	126	127	129	130	131	132	82	83	83	84	85	85	86

Source: Adapted from: The Fourth Report on the Diagnosis, Evaluation, and Treatment of High Blood Pressure in Children and Adolescents; NIH Publication No. 05-5267.

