## **6.2 Management of toxicity (other than hand-foot skin reaction, hypertension and LFT abnormalities)**

The table below outlines dose adjustments for **most hematologic and non-hematologic toxicities related to regorafenib** except hand-foot skin reaction (HFSR) and hypertension and LFT abnormalities.

In addition to these recommended dose modifications, subjects who develop diarrhea (see

Section 6.6), mucositis, anorexia or other events predisposing to fluid loss or inadequate fluid intake should be carefully monitored and rehydrated as clinically necessary. This is in order to minimize the risk of postural hypotension and renal failure.

**Table 6.2 Recommended dose modification for most toxicities, except hand-foot skin reaction, hypertension and ALT/AST/bilirubin**

NCI-CTCAE v 4.03 a	Dose Interruption	Dose Modification b	Dose for Subsequent Cycles
Grade (G) 0-2	Treat on time	No change	No change
G 3	Delay until $\leq$ G 2 c	Reduce by 1 dose level	If toxicity remains < G2, dose re-escalation can be considered at the discretion of the treating investigator. If dose is re-escalated and toxicity ( $\geq$ G3) recurs, institute permanent dose reduction.
G 4	Delay until $\leq$ G 2 c	At a minimum, reduce by 1 dose level.  Strongly consider permanent discontinuation for G4 events such as: gastrointestinal perforation/fistula, severe or life-threatening hemorrhage, reversible posterior leukoencephalopathy syndrome, or wound dehiscence.	

a. G: Grade; NCI-CTCAE = National Cancer Institute - Common Terminology Criteria for Adverse Events, version 4.03
 
b. Excludes alopecia, non-refractory nausea/vomiting, non-refractory hypersensitivity and nonclinical and asymptomatic laboratory abnormalities.
 
c. If no recovery after a 4 week delay, treatment should be permanently discontinued unless subject is deriving clinical benefit and is discussed with the SARC Medical Officer.
			

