**Table 6.3.2 Recommended dose modification for hand-foot-skin reactiona**

Grade of event (NCI-CTCAE v 4.03)	Occurrence	Suggested Dose Modification
Grade (G) 1	Any	Maintain dose level and immediately institute supportive measures for symptomatic relief
G 2	1 st occurrence	Consider decreasing dose by one dose level and immediately institute supportive measures. If no improvement, interrupt therapy for a minimum of 7 days, until toxicity resolves to G 0-1 b, c
	No improvement within 7 days or 2 nd occurrence	Interrupt therapy until toxicity resolves to G 0-1. c When resuming treatment, decrease dose by one dose level b
	3 rd occurrence	Interrupt therapy until toxicity resolves to G 0-1. c When resuming treatment, decrease dose by one dose level. b, d
	4 th occurrence	Discontinue therapy
G 3	1 st occurrence	Institute supportive measures immediately. Interrupt therapy for a minimum of 7 days until toxicity resolves to G 0-1. c When resuming treatment, decrease dose by one dose level. b, d
	2 nd occurrence	Institute supportive measures immediately. Interrupt therapy for a minimum of 7 days until toxicity resolves to G 0-1. c When resuming treatment, decrease dose by one additional dose level b, d
	3 rd occurrence	Discontinue treatment permanently.

a. More conservative management is allowed if judged medically appropriate by the investigator.
 
b. If toxicity returns to G 0-1 after dose reduction, dose re-escalation is permitted at the discretion of the investigator if subject has completed one cycle at reduced dose without recurrence of event.
 
c. If there is no recovery after a 4 week delay, treatment with regorafenib or placebo will be discontinued permanently.
 
d. Subjects requiring > 2 dose reductions should go off protocol therapy.
 
e. The maximum daily dose is 160 mg
		

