**Table 6.5.1 Recommended measures and dose modification in case of drug-related liver function test abnormalities**

Observed elevations of ALT and/or AST	Occurrence	Recommended measures and dose modification
≤ 5 times upper limit of normal ULN (maximum Grade 2)	Any occurrence	Continue regorafenib or placebo treatment.  Monitor liver function weekly until transaminases return to < 3 times ULN (Grade 1) or baseline.
>5 times ULN to ≤ 20 times ULN (Grade 3)	1 st occurrence	Interrupt regorafenib or placebo treatment.  Monitor transaminases weekly until return to < 3 times ULN or baseline.  Restart: If the potential benefit outweighs the risk of hepatotoxicity, re-initiate regorafenib or placebo treatment, reduce dose by 40 mg (one tablet), and monitor liver function weekly for at least 4 weeks.
	Re-occurrence	Discontinue treatment with regorafenib or placebo permanently.
> 20 times ULN (Grade 4)	Any occurrence	Discontinue treatment with regorafenib or placebo permanently.
> 3 times ULN (Grade 2 or higher) with concurrent hyperbilirubinemia > 2 times ULN		Discontinue treatment with regorafenib or placebo permanently.  Monitor liver function weekly until resolution to < 3 times ULN or return to baseline.  Exception: patients with Gilbert syndrome who develop elevated transaminases should be managed as per the above outlined recommendations for the respective elevation of ALT and/or AST.

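### Table 6.4.2's full-dose restart after a paediatric hypertension hold names no dose level and, read literally, can undo an earlier reduction for another toxicity

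*Combined protocol and SAP*

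**What the plan says.** Table 6.4.2 covers paediatric hypertension. For symptomatic Grade 2 or Grade 3 it holds the drug until symptoms and blood pressure settle, then says "Resume study at 100% (full) dose", followed by "If similar toxicity recurs, discontinue study drug". It has no step that reduces the dose.

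Table 6.4.1, for adults, words the restart differently in both the Grade 2 and Grade 3 rows: "When regorafenib or placebo is restarted, continue at the same dose level".

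Section 6.4 introduces both tables with "Every effort should be made to control blood pressure by medical means other than study drug dose modification".

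Table 6.1.2 defines the paediatric levels as 82 (level 0, the standard starting dose), 72 (level -1) and 60 mg/m² (level -2), each rounded to the nearest 20 mg. Section 6.1 caps the dose at 160 mg and says modifications follow the predefined levels. Neither place uses a percentage or defines a full dose.

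Other toxicities have their own rules for going back up:
- Table 6.2: if the toxicity stays below Grade 2, "dose re-escalation can be considered at the discretion of the treating investigator". If Grade 3 or worse returns after that, the reduction is permanent.
- Table 6.3.2 (hand-foot skin reaction), once the reaction is back to Grade 0-1: "dose re-escalation is permitted at the discretion of the investigator if subject has completed one cycle at reduced dose without recurrence of event".
- Table 6.5.1 (liver tests), after a first Grade 3 transaminase rise: "re-initiate regorafenib or placebo treatment, reduce dose by 40 mg (one tablet), and monitor liver function weekly for at least 4 weeks". No re-escalation is mentioned, and Table 6.2 cannot supply it, because its scope is most toxicities "except hand-foot skin reaction (HFSR) and hypertension and LFT abnormalities".

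**The concern.** The paediatric restart instruction is not tied to a dose level and makes no provision for a child whose dose is already reduced. Taken at its word, it sends that child back to level 0 straight after a hold for a second toxicity, whatever the state of the first. Two sites could also dose the same child differently. Children can enter cohort D from age 5 and cohort E from age 10, and these are the cohorts that sections 2.5 and 3.1 leave open to accrual. What is at stake is dosing safety in a small number of children, not the statistical design.

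**Working it through.** The plan gives no figure on this point, so the check has three parts.

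**1. Where the literal reading conflicts with another rule**
- Table 6.2 reduction: conflict if the earlier toxicity is still Grade 2, or if an earlier re-escalation failed and the reduction is permanent.
- Table 6.3.2 reduction: conflict if the reaction is not back to Grade 0-1, or if one cycle at the reduced dose without recurrence has not been completed.
- Table 6.5.1 cut: conflict in every case, since no way back up is provided.
- Otherwise re-escalation is already allowed at the investigator's discretion, and there is no conflict.

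The multiple-toxicity rule below Table 6.1.2 says how far to reduce. It is silent on the restart dose, so it does not settle the question.

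**2. Size of the step**

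Daily dose = body surface area (BSA) × level, rounded to the nearest 20 mg, at most 160 mg. Nominal step from level -1 to level 0: 82/72 = 1.139, or +14%.

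| BSA (m²) | Level 0 | Level -1 | Literal step from level -1 |
|---|---|---|---|
| 0.65 (minimum) | 53.3 → 60 mg | 46.8 → 40 mg | +20 mg |
| 1.00 | 82 → 80 mg | 72 → 80 mg | none |
| 1.40 | 114.8 → 120 mg | 100.8 → 100 mg | +20 mg |

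Over an assumed BSA range of 0.65 to 2.00 m², not weighted by patients, the two rounded doses differ in about 66% of the range, always by 20 mg.

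The liver cut is a flat 40 mg, not one paediatric level, so its reversal is larger:
- BSA 1.00 m²: 80 - 40 = 40 mg. A full restart goes from 40 to 80 mg, which doubles the dose.
- BSA 1.40 m²: 120 - 40 = 80 mg. A full restart goes from 80 to 120 mg, or +50%.

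Level -2 is also permitted, and from there the nominal step is 82/60 = 1.367, or +37%. No child in the phase I trial had more than one reduction.

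**3. How often**

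The documents give no joint figure. Section 2.4.3 gives these margins from 41 treated children, pooled over 60 to 93 mg/m²:
- Dose reductions: 14/41 (34.1%).
- Grade 3 or higher hypertension: not in the list of events above 5%. Since 3/41 = 7.3% would be listed, at most 2/41 = 4.9%.
- Drug-related hypertension of any grade: not in the list of events at 20% or more. Since 9/41 = 22.0% would be listed, at most 8/41 = 19.5%.

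Assuming these rates, independence, and that all 24 patients in cohorts D and E are children:
- Through Grade 3 hypertension: 24 × 2/41 × 14/41 = 0.40 child.
- If every drug-related hypertension of any grade led to a hold: 24 × 8/41 × 14/41 = 1.60. This is a loose ceiling, because Grade 1 and asymptomatic Grade 2 are not held.
- If half are children: 0.20 and 0.80.
- Without independence, if every child with Grade 3 hypertension had already been reduced: 24 × 2/41 = 1.2.

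These are ceilings on observed phase I proportions and carry the sampling error of 41 children. They count every reduced child, including those for whom re-escalation is already allowed, those reduced only after the hold, and those for whom rounding removes the step. The number with a true conflict is therefore smaller.

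**The case against.** The best reply is that the milder reading is the natural one. Table 6.4.2 deals with one toxicity and offers only no change, hold and resume, or stop. In that setting a full-dose restart may simply mean that the dose is not cut for the hypertension, which fits section 6.4's preference for controlling blood pressure by other means. Nothing in the table claims to override the rules for other toxicities. Section 6.4 also leaves management to local standards and the investigator's usual practice, and calls its dose reductions suggested. The literal outcome never exceeds 82 mg/m², the recommended paediatric phase II dose. The only hypertension dose-limiting toxicity listed was at 93 mg/m². Recurrence stops the drug, which is stricter than the adult step-down.

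Most of this stands, and it limits the point. A reader might infer that the plan orders children back to full dose over an unresolved toxicity. The documents do not support that, because the milder reading is open and investigators keep discretion. Nor does the literal reading break a rule for every reduced child, or take anyone above the tested paediatric dose.

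What does not stand is that the text settles the matter. The milder reading is nowhere written, the word full points towards the unreduced dose, and the adult table shows how the clear version would read. The stop rule refers to similar toxicity, which most naturally means the hypertension and does not clearly cover a return of the first toxicity.

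**Conclusion.** The point holds as a minor safety correction. Table 6.4.2 states a restart rule that, followed as written, can return a reduced child to the starting dose, bypass the conditions in Tables 6.2 and 6.3.2, and reverse a liver-test cut that has no re-escalation provision. On the literal reading the increase is zero or 20 mg from level -1 and 40 mg after a liver cut. On the milder reading it is nil.

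The situation is uncommon: at most about 0.4 child through Grade 3 hypertension, and fewer with a true conflict. That rests on phase I rates, independence and all 24 patients being children. Wide variation in exposure between children could make toxicities cluster and raise the figure, while a lower share of children would reduce it. A reader might look for an effect on sample size, power or endpoints; nothing in the documents points to one, and none is claimed.

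**What to change.** Replace the sentence in Table 6.4.2 with: *Resume study drug at the same dose level as before the hold.* This matches Table 6.4.1 and leaves the re-escalation rules in Tables 6.2 and 6.3.2 as they are. For a child cut by 40 mg under Table 6.5.1, whose dose need not be a Table 6.1.2 level, it should be understood as the daily dose in use at the hold. The sentence should not add a general re-escalation clause: Table 6.5.1 has no such rule, so the clause would quietly make liver cuts permanent. If a return to level 0 is really intended for a reduced child, the table should say so and give the reason.

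The cost is one sentence. Amendment approvals have to be documented for each of about 18 centres, so the change is best bundled with the next amendment.
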